### Exclusion Criteria (note that we are no longer excluding Veterans with specific health issues)

- Non-Veterans
- A documented current history of active psychosis or other cognitive issues via ICD-10 codes
- Has participated in  $\geq 4$  MOVE! sessions in the past year
- Pregnancy

- PCP stating that Veteran should not participate
- Self-reported inability to read at a 5th grade level due to literacy level or vision problems

With an expected 20% participation rate (based on pilot data) and a 75% retention rate (based on rates from another VA study and other technology-based interventions), we will need to screen 2,615 Veterans with overweight/obesity to enroll a baseline sample of up to 520 Veterans and end with 392 Veterans completing the study. With a screening rate of approximately 30-35 Veterans per week (6 women, 24 men), we will be able to recruit our target population by the middle of Year 3 (recruitment will start the first quarter of Year 2).

Study Arms/Randomization – Under the direction of the study statistician, the PACT teams will be randomized at the provider level using a random number generator to either the PAL Intervention or Enhanced Usual Care intervention arms.

- *PAL Intervention group:* Participants will arrive and complete consenting materials, a Baseline Survey, and the GEM tool. They will then have a brief break if needed. After the break, they will work collaboratively with the Health Coach using tool-generated materials to modify their goals into SMART goals (specific, measurable, attainable relevant, and timely). The patient will then receive materials containing an individualized report with a summary of their personalized advice, initial goals, and barriers and facilitators to weight loss. They will also receive a packet of MOVE! handouts tailored to their questionnaire responses and schedule 10-12 follow-up health coaching phone calls during the next 12 months of intervention. The Health Coach will also inform the patient of the resources available to them at the VA (e.g. MOVE, TeleMOVE!) that can assist them in achieving their goals.

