Telephone Coaching/Self-Monitoring Visit – To achieve sufficient intensity according to VA/DOD and USPSTF guidelines, we will incorporate 12 telephone coaching calls by a health coach over 12 months. Scheduled calls will occur two weeks and four weeks post-baseline, then once every month for the remainder of the study. PAL Intervention arm Veterans will receive a reminder call to self-monitor their weight, food intake, and PA for at least 3 days prior to the coaching call. Studies suggest that episodes of short, consistent self-monitoring (for 3 days) lead to weight loss and may promote better adherence. Health coaches will use self-reported self-monitoring data to determine goal adherence and counsel Veterans to encourage small changes. Data from health coaching sessions will be documented in REDCap, our research database. They will help Veterans create new goals when appropriate and use MI techniques to address barriers to behavior change. Veterans will be able to contact health coaches for additional support.

CPRS Research Note/Reminders– The PAL tool creates a provider report that the health coach will cut and paste into CPRS as a research note to summarize and communicate information to the Veteran's PACT team about the health coach session. This note generates a CPRS reminder for the PCP. The reminder facilitates documentation about whether the PACT team discussed goals and provided further counseling. This research note and reminder system will also be used to document both health coach telephone counseling and PACT counseling during future PC visits.

PACT Team Role – PACT teams randomized to the intervention arm will provide at least 3-5 minutes of counseling. They will choose who on the team counsels (based on formative data indicating variability in team member roles). They will document counseling with the help of CPRS reminders, provide brief MI to address barriers (depending on time and Veteran needs), and briefly discuss weight management goals during future PC visits. Each PACT team dietitian will co-sign the health coach CPRS note and will be available as a resource. Health coaches will attend PACT meetings to communicate the progress of enrolled Veterans. They will also communicate PACT team barriers to the PI.

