**Intermediate Outcomes:** Our intermediate outcomes are based on the theory of planned behavior  where motivation and intention to perform a behavior, mediated by self- efficacy, predict behavior change. These constructs will be measured with previously used items that have been adapted for our survey measures by adding other elements of the Theory of Planned Behavior including behavioral beliefs, attitudes, subjective norms, and perceived behavioral control. We will also assess goal attainment at 6 and 12 months.

**Physical Activity (PA) Outcomes:** We will measure duration and intensity using the International Physical Activity Questionnaire (IPAQ) items and accelerometers. The ActiGraph Link (GT9X) accelerometer, worn on the wrist, will be used to objectively measure PA for 7 days at Baseline, and at 6 and 12 months. Study staff will place the Link monitor on the non-dominant wrist to measure PA for 24 hours a day during the Baseline 7-day measurement period. Veterans will then mail the monitor back to the study team in a supplied mailer with postage. At 6 and 12 months, the accelerometer will be distributed to the Veteran with a supplied mailer with postage to be mailed back to the study team. Veterans will not be able to see their data on these monitors so as to minimize measurement influence on PA behaviors. This approach has been used in the NHANES Physical Activity Monitor study. The acceleration data will be used to characterize PA behavior. Examples of PA behavior include steps per day, ambulatory time, as well as daily sum of vector magnitude units per day. The daily sum of vector magnitude units are a quantification of all movement including ambulatory and non-ambulatory activity.

**Behavioral Outcomes:** We will assess diet and physical activity behaviors at Baseline and again at 6 and 12 months. Our main dietary outcomes will be servings of fruits and vegetables, fat intake, refined carbohydrates, and sweetened beverage intake via surveys. A subset of up to 20 participants will complete 24-hour dietary recalls, and this will allow us to assess total energy intake and energy density in this subgroup. Physical activity outcomes will be changes in duration and intensity. We will use chart review to evaluate attendance to TeleMOVE! or MOVE! (# of sessions) pre- and post-baseline visit and 6 and 12 months post- intervention.

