Treatment Fidelity: We will do detailed chart reviews using a chart abstraction tool to monitor how often providers see patients and document goal-setting discussions during subsequent visits after the index visit.

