### 2. Identify predictors of weight loss in Veterans participating in the intervention arm related to intervention components and goal-setting processes

2a: Participation in MOVE!, number of telephone coaching calls received, the use of self-monitoring, and counseling by PACT teams will be associated with weight loss.

2b: Veteran self-efficacy and goal attainment will be associated with weight loss.

Method: Visualization tools such as scatterplots and descriptive analyses such as Spearman correlation coefficients will be used to display associations between weight change and potential predictors. Multivariate regression models will be used to examine the effects of those predictors that are suspected to be associated with weight loss in the intervention arm. Multivariate linear regression models will be considered for continuous outcomes and multiple logistic regression models will be considered for binary outcomes. We will construct classification and regression trees (CARTs), which will generate the variable importance for each intervention component. Missing data will be dealt with using inverse-probability-weighted methods.

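### Aim 2 will report CART variable importance for each intervention component without naming the importance measure, pruning or predictor coding; the standard measure favours predictors with more cut points

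*Combined protocol and SAP*

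**What the plan says.** One study objective is to identify predictors of weight loss in the intervention arm related to goal setting and intervention components. The Specific Aims Analysis, item 2, lists the candidates. Hypothesis 2a reads "Participation in MOVE!, number of telephone coaching calls received, the use of self-monitoring, and counseling by PACT teams will be associated with weight loss", and hypothesis 2b reads "Veteran self-efficacy and goal attainment will be associated with weight loss".

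The Method paragraph plans scatterplots, Spearman correlations, multivariable linear and logistic regression, and then: "We will construct classification and regression trees (CARTs), which will generate the variable importance for each intervention component". It does not give the splitting rule, the stopping or pruning rule, the importance measure, any validation, or the coding of the predictors. No other section supplies these. The paragraph does not say that components will be ranked.

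**The concern.** At each node, a standard regression tree tries every cut point of every predictor and keeps the split with the largest drop in variance. A yes/no predictor has one cut point. A count from 0 to 12 has up to 12, so it has more chances of a large drop by luck alone. Importance computed as the sum of these drops inherits that advantage.

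The Aim 2 predictors may differ widely in number of levels, and in hypothesis 2a only the calls are worded as a number. Importance values set side by side, one per component, will be read as an order of merit whether or not the plan uses that word. A component with a real association could then look unimportant because it was recorded coarsely, and one with no association could look important because it was recorded finely.

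**Working it through.** The plan gives no figure for this analysis, so there is none to reproduce. The check is by simulation.

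**Inputs from the documents**
- Completers: 392 at 12 months (Sample Size and Power Analysis). With equal arms, 392 / 2 = 196 in the PAL arm.
- SD of weight change: 6.0 kg (same section).
- Calls: "we will incorporate 12 telephone coaching calls by a health coach over 12 months" (Telephone Coaching/Self-Monitoring Visit), so 0-12 and at most 12 cut points. The Study Arms text has participants "schedule 10-12 follow-up health coaching phone calls during the next 12 months of intervention"; if nearly everyone receives 10-12, only 2 cut points remain.
- MOVE! attendance: collected as a number of sessions (Behavioral Outcomes).
- PACT counseling: chart review will "monitor how often providers see patients and document goal-setting discussions during subsequent visits after the index visit" (Treatment Fidelity), so a count is possible.
- Self-monitoring: participants are prompted to "self-monitor their weight, food intake, and PA for at least 3 days prior to the coaching call", so it could be yes/no or a count up to 12.
- Self-efficacy and goal attainment: no scale stated.

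**Assumptions, because the documents are silent:** the coding of each predictor, the distribution of calls, 25% attending MOVE!, independent predictors, and the tree settings.

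**Formula.** For a cut point c, gain(c) = SS(node) - SS(left) - SS(right). The split taken is the maximum over all predictors and cut points. Importance of a predictor = sum of gain over its splits. With complexity parameter cp, a split is kept only if its gain is at least cp times the total SS.

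**Hand check of the mechanism.** For one null yes/no predictor, n × R² is about chi-square with 1 df. At cp = 0.01 the threshold is 196 × 0.01 = 1.96, which is passed with probability 0.16. All three yes/no predictors fail with probability (1 - 0.16)³ = 0.59. The simulated tree has no split in 23% of runs, so calls must fail in about 0.23 / 0.59 = 0.39 of runs and pass in about 0.61. Calls therefore clear the threshold nearly four times as often as a yes/no component, with no effect anywhere. At cp = 0.03 the threshold is 196 × 0.03 = 5.88, which a yes/no predictor passes with probability 0.015.

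**Simulation, no true effects** (n = 196, 400 replicates per setting; Monte Carlo error about √(0.6 × 0.4 / 400) = 2.4 points). Entries are the percentage of runs in which calls has the highest importance.

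| Coding | Fair share | cp = 0.01 | Single split | Fully grown |
|---|---|---|---|---|
| (a) Calls 0-12, other three components yes/no | 25 | 60 | 67 | 98 |
| (b) MOVE! and PACT counseling as counts, self-monitoring yes/no | 25 | 48 | 42 | 77 |
| (c) All four as counts, self-monitoring 0-12 | 25 | 32 (self-monitoring 43) | | 42 (self-monitoring 52) |
| (d) As (a), plus 5-level self-efficacy and yes/no goal attainment | 17 | 58 | | |
| (e) As (a), plus 41-level self-efficacy and 0-100 goal attainment | 17 | 14 (the two scores 85) | | 5 |
| (f) Calls confined to 10-12, others yes/no | 25 | 23 | | 52 |

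In (a) at cp = 0.01, 60 / (100 - 23) = 78% of trees that split put calls first. A second set of runs with other tree settings gave 66-89% for (a), about 50% for (b), and 27% for (f) at cp = 0.01. At cp = 0.03, 42-93% of runs had no split, depending on coding, and calls came first in 2-10%.

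**Simulation, one true effect and none of calls**
- MOVE! yes/no, true effect 2.2 kg, coding (a), 1,000 replicates: calls first in 52% at cp = 0.01 (MOVE! 37%) and in 96% fully grown (MOVE! 2%). With a 3.5 kg effect at cp = 0.01, MOVE! leads, 75% to 23%.
- MOVE! as sessions, true effect 2.2 kg, coding (b): MOVE! 49% and calls 34% at cp = 0.01; MOVE! 15% and calls 71% fully grown.
- PACT counseling yes/no, true effect 2 kg: calls outranks it in 56-75% of runs, and in 63-87% in another set with different tree settings. In the latter set, ordering components by |t| from a multivariable regression put PACT counseling first in 79-80%.

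**After correction.** With predictors ordered by the permutation p-value of their best split (no true effects, 300 replicates), calls came first in 27% under (a) and 24-26% under count coding, against 25%. With six predictors it came first in 14-19%, against 17%. This tests the principle behind conditional-inference trees; a full conditional-inference forest was not run.

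**The case against.** The strongest reply is that the direction of the bias is not known. No section codes self-monitoring or PACT counseling as yes/no, MOVE! attendance is a session count, and calls may cluster at 10-12. If the 2b measures enter as long scores, they rise to the top and calls falls to 14%. A reader might infer that the number of calls will usually lead whatever the truth. The documents do not support that, because it needs calls to have the most levels and the tree to be lightly pruned, and neither is fixed. This part of the reply stands.

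Pruning also matters. At cp = 0.03 most null trees are empty under several codings and yield no importance at all. That limits the harm under no effect, but the plan does not say that it will prune, and an empty tree does not deliver the promised output either.

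Finally, the plan announces no ranking, and it runs correlations and regression on the same predictors. It would go too far to say that CART alone decides which components matter. Regression fits one coefficient per predictor and searches no cut points, so it does not have this bias. It does not, however, correct an importance table reported beside it.

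The alternative codings do not remove the defect. In (c), calls and self-monitoring together take 32 + 43 = 75% against a fair share of 50%. In (e), the two long scores take 85% against 33%. The favoured variable changes, but importance still follows the number of levels.

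**Conclusion.** The concern holds in conditional form. As written, Aim 2 commits to an importance figure per component whose standard version depends partly on how finely each predictor is recorded, and the plan has no safeguard.

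If calls is the only many-level component, it leads in about 60-90% of lightly pruned or unpruned null trees (98% fully grown). If MOVE! and PACT counseling are counts, it leads in about 40-50% (77% fully grown). The fair share is 25%. With yes/no coding, calls can outrank a component with a true effect of about 2 kg in more than half of trials. The advantage mostly goes at light pruning if calls cluster at 10-12, and it passes to self-efficacy or goal attainment if those have more levels.

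These sizes rest on assumed codings and distributions, independent predictors and equal arms. The existence of the bias does not rest on the particular coding, as long as the predictors differ in number of levels. The point concerns a secondary aim in one arm. It does not touch the 12-month weight comparison or the power statement.

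**What to change.** In the Method paragraph of Aim 2, adopt one of the following:
- Obtain component importance from conditional-inference trees or forests, which choose splits by permutation test, and report permutation importance.
- Base statements about which components matter on the estimates and confidence intervals from the regression already planned, and label CART importance as illustrative only.

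In either case, state in advance how each predictor is coded, whether the 2b measures enter the tree, and how the tree is pruned and validated.

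The cost is a few sentences of analysis-plan text, a different software routine and slightly more analysis work. Design, data collection and sample size do not change.

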### 3. Determine the impact of the PAL Intervention on provider and nurse obesity-related counseling practices and attitudes

3a: Veterans in the PAL intervention arm will receive more frequent and higher quality weight management counseling from PCPs than those in the control arm. The intervention will improve PCP self-efficacy, attitudes, and perceived competency in weight management counseling.

Method: Mann-Whitney tests for continuous provider-level outcomes and Fisher's exact tests for categorical provider-level outcomes will be used to compare the two intervention arms at each survey. Confidence intervals of the effects will be computed as well.

Missing Data Analysis (to adjust for response bias) -- Although the repeated measures modeling can address missing data automatically under the assumption of missing-at-random, we will further analyze the missing data due to loss of follow-up or non-response using two popular missing data tools, inverse-probability-weighting approach and multiple-imputations approach. Both missing data approaches utilize the baseline characteristics to adjust for response bias. In addition, we will use multiple-imputations procedure to conduct sensitivity analyses under the practical assumption of missing not at random. Specifically, the sensitivity analyses will be conducted using pattern-mixture models to examine if statistical findings are robust when considering several scenarios, including the least-favorable scenario where missing data from the intervention arm were to follow the same pattern as that of the observed data from the Enhanced Usual Care arm.

Sample Size and Power Analysis – We base our sample size on within-person weight change at Baseline and 12 months in each arm. We assume an interclass correlation coefficient (ICC) of 0.05 for Veterans within each PCP and an ICC of 0.01 for PCPs within each PACT team. Assuming that at the end of the study we have 5 teams in each intervention arm and recruit and obtain baseline data for 52 Veterans per PACT team (392 Veterans total at 12 months), we will have sufficient power to detect a 2.2kg (SD=6.0kg) difference in weight between the intervention and non-intervention arms. If we do not have PACT attrition (5 PACT teams per arm), then we will have additional power. This amount of weight loss is consistent with findings from the ASPIRE VA study and a systematic review of technology-assisted weight loss interventions in primary care. We will also have the power to detect our hypothesized difference of 15% of PAL Intervention Veterans achieving 5% weight loss (clinically significant—as little as 5% weight loss can improve cardiovascular risk), 85% assuming 12% of intervention arm Veterans achieve this amount of weight loss. We will be able to detect 2.9cm change in waist circumference.

If we assume the missing rate at 12 months is 15%, then we will have 44 evaluable Veterans per team. We assume an interclass correlation coefficient (ICC) of 0.03-0.04 for Veterans within each PACT team and an ICC of 0.01 for PCPs within each team. If the ICC of Veterans within each PACT team is 0.03, the power is 85% to detect a 2.2kg (SD=6.0kg) difference in weight between the intervention and intervention arms; the power is 87% to detect a 2.9cm (SD=7.7cm) difference in waist circumference. This amount of weight loss and waist circumference change is consistent with findings from the ASPIRE VA study and a systematic review of technology-assisted weight loss interventions in primary care. In addition, the power is 91% to detect our hypothesized difference between 25% Veterans in the intervention arm and 10% of Veterans in the control arm achieving 5% weight loss (clinically significant). If the ICC of Veterans within each PACT is 0.04, the powers are 81%, 83%, and 87% to detect the same effect sizes of weight loss, waist circumference, and proportion of 5% weight loss, respectively.

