#### Project Methods

To achieve these objectives, we will conduct a cluster randomized controlled trial of 17 PACTs (randomized at the provider level) and 520 of their overweight or obese Veteran patients at the Brooklyn campus of the NY Harbor Healthcare System to study the impact of the 12-month PAL intervention when compared to Enhanced Usual Care. Patients in the PAL intervention will complete the GEM tool and receive health coaching, followed by telephone coaching from the health coach over 12 months. The GEM

tool is a mobile-friendly software program designed to be delivered on tablet computers in the clinic setting to assess lifestyle behaviors and barriers, provide tailored advice and patient education materials, create initial weight loss and behavior change goals, and facilitate counseling by the health coach and PACT staff. Patients in the Enhanced Usual Care arm will receive patient education materials (standard VA Healthy Living Messages) and information on the MOVE! program. All patient participants will attend follow-up visits at 6- and 12-months to assess Body Mass Index, waist circumference, blood pressure, diet, blood tests, physical activity, and goal attainment. PACT staff and health coach outcomes will include 5As-related competency, as well as quality and frequency of counseling. If circumstances restrict the availability of in-person visits (e.g. COVID-19) or based on Veteran's preference, this study will provide a remote/tele-visit option for the baseline and follow up visits.

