We will conduct several statistical analyses to describe Veterans participating in the study. Descriptive statistics, including numerical summaries, frequency tables and graphical displays, will be used to present baseline participant characteristics. Exploratory tests, such as chi-square tests and t-tests, will be used to investigate if baseline characteristics are balanced between two randomized arms. Analysis of missing data due to dropout or incomplete surveys will be investigated by inferring a relationship between baseline characteristics/risk factors and 0-1 indicator that defines whether or not a measurement is observed. This analysis will help to identify factors that are likely to be associated with dropout. Additionally, we will investigate whether the dropout rates are different between two arms. For instance, participants with higher levels of motivation may be more likely to be retained in the study. To deal with these missing, we will incorporate the multiple imputation procedure with the regression analyses to be discussed in the following, along with some sensitivity analysis.

In order to assess the impact of neighborhood-level covariates that may help predict weight loss and behavior change, as well as to better understand and report the environmental context of our study participants, we will determine the Veteran's census tracts and block groups. To do this, we will send a csv file containing the patients' addresses to the VA's geocoding service, Geospatial Service Support Center (GSSC), which uses VA's secured proprietary Enterprise Geographic Information System (GIS) software (<https://www.va.gov/oei/docs/va-spatial-data-strategy.pdf>), via the VA's encrypted email. The data will not include the patient's name or apartment number. GSSC will process the data and return a copy of the spreadsheet with the census tract and block group codes added. Once the data is geocoded, the addresses will be purged from the GSSC's database. All applications of geospatial data will be compliant with the objectives and standards established under the VA Spatial Data Strategy (2022).

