## STATISTICAL AND DATA ANALYSIS

First, all the variables will be summarized (intention-to-treat approach) using mean (with standard deviation) and median (with interquartile range for continuous variables and frequency table for categorical variables) overall and by interventions arms, respectively. Then, Mann-Whitney tests for continuous variables and Fisher's exact tests for categorical variables will be used to check if both providers' and Veterans' baseline characteristics are balanced between the intervention arms.

Specific Aims Analysis (main outcomes will be analyzed using intention-to-treat methodology).

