### 1. Test the impact of the PAL intervention on weight change, clinical, and behavioral outcomes

1a: Veterans in the PAL Intervention arm will lose 2.2 kg and 27% will achieve  $\geq 5\%$  weight loss after 12 months of treatment. There will be 0kg weight change in the Enhanced Usual Care arm, and 12% will achieve  $\geq 5\%$  weight loss.

1b: The PAL Intervention will result in improvements in behavioral outcomes (e.g., increased number of steps, increased fruit/vegetable intake, increased attendance to MOVE!) and clinical outcomes (blood pressure, Low Density Lipoprotein (LDL), Hemoglobin A1C, and waist circumference).

1c: The PAL Intervention will increase attendance to MOVE! and/or other intensive programs.

Method: The primary outcome is mean weight loss at 12 months. Mann-Whitney tests for continuous outcomes (e.g., weight loss) and Fisher's exact tests for categorical outcomes (e.g., whether or not Veterans achieve  $\geq 5\%$  weight loss) will be used to compare the two intervention arms at 12 months, respectively. Unadjusted confidence intervals will be computed to measure the effects of the PAL intervention on the outcomes compared with the Enhanced Usual Care. Repeated measures modeling based on mixed models will be conducted to compare outcome variables between intervention arms, utilizing all of the data at Baseline and at follow-up visits. Such modeling can adjust for baseline characteristics (e.g., diabetes, gender), taking into account: a) the correlation among Veterans within providers, b) the correlation among repeated measures within Veterans. Model-based adjusted confidence intervals will be provided to measure the effects of the intervention on the outcomes as well. Although repeated measures modeling can address missing data automatically, assuming it is missing at random, we will use a multiple imputation procedure to conduct sensitivity analyses under the practical assumption of missing not at random. The sensitivity analyses will be conducted using pattern-mixture models to examine if the statistical findings are robust when considering several scenarios, including the least-favorable scenario where the missing data from the PAL intervention arm were to follow the same pattern as that of the observed data from the Enhanced Usual Care arm.

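### The missing-at-random multiple imputation is described without a provider effect; run that way, its intervals would be roughly 5-13% too narrow at the plan's own ICCs

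*Combined protocol and SAP*

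**What the plan says.** Project Methods describes a "cluster randomized controlled trial of 17 PACTs (randomized at the provider level"). The first paragraph of the Sample Size and Power Analysis states "We assume an interclass correlation coefficient (ICC) of 0.05 for Veterans within each PCP"; the second uses 0.03 to 0.04 within team. The Aim 1 method has a mixed model that allows for "the correlation among Veterans within providers" and handles missing data under missing at random without imputing anything.

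Multiple imputation comes in at three places:

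- Data Analysis, on dropout and incomplete surveys: "we will incorporate the multiple imputation procedure with the regression analyses to be discussed in the following". The imputation model is not described.
- Aim 1 method: "we will use a multiple imputation procedure to conduct sensitivity analyses under the practical assumption of missing not at random". One pattern-mixture scenario is named, in which missing PAL data follow the pattern observed in Enhanced Usual Care.
- Missing Data Analysis under Aim 3: weighting and imputation are added as further analyses, and "Both missing data approaches utilize the baseline characteristics to adjust for response bias". The same named scenario is then repeated.

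Baseline characteristics are the only stated input to the imputation. None of these places mentions a provider or cluster term.

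**The concern.** An imputation model should carry the dependence that the analysis model is meant to estimate. Here Veterans of one provider share part of their weight change. If provider is absent from the imputation, a missing weight is drawn around the arm average instead of around what that provider's other Veterans show. The filled-in values pull provider means toward the arm mean, and the analysis then finds less between-provider variance than there is. This is a different fault from a test that ignores clustering, because the analysis model can be right and the pooled interval still too short.

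At stake is the precision of the missing-at-random imputed analyses. A reader comparing them with the mixed model would see tighter intervals that come from how the gaps were filled, not from added information.

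**Working it through.** **The plan's own figures.** The documents give no standard error or interval width for an imputed analysis. The nearest figure is the power for 2.2 kg (SD 6.0) with 15% missing: 85% at ICC 0.03 and 81% at ICC 0.04. Ten clusters of 22 per arm reproduce both:

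- ICC 0.03: design effect 1 + 21 × 0.03 = 1.63; effective n 220/1.63 = 135.0 per arm; SE = 6 × √(2/135.0) = 0.730; power = Φ(2.2/0.730 − 1.96) = 85.4%.
- ICC 0.04: design effect 1.84; effective n 119.6; SE 0.776; power 80.9%.

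(Read literally, 5 teams of 44 per arm gives 71.9% and 64.5%. That mismatch is a separate matter.) The plan's power therefore does rest on clustering at these ICCs.

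**Inputs.** 17 providers and 520 Veterans (Project Methods), so 520/17 = 30.6, taken as m = 31 per provider. ICC 0.03 to 0.05 (Sample Size and Power Analysis). Missing fraction f = 0.15 (same section) or 0.25 (75% retention, in the text after the Veteran exclusion criteria). Two-sided 5% is assumed, since no alpha is stated.

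**Closed form**, per provider, in units of SD²:

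- True variance of an observed provider mean: T = ICC + (1 − ICC)/(m(1 − f)).
- Rubin variance when imputation ignores provider: R = (1 − f)² × ICC + 1/(m(1 − f)). Only (1 − f)² of the between-provider part survives.

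Example, ICC 0.05 and f = 0.25: m(1 − f) = 23.25; T = 0.05 + 0.95/23.25 = 0.0909; R = 0.5625 × 0.05 + 1/23.25 = 0.0711; SE ratio = √(0.0711/0.0909) = 0.885.

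R leaves out a small term. Subtracting (1 − f) × ICC/m, here 0.75 × 0.05/31 = 0.0012, gives R = 0.0699 and a ratio of 0.877.

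| ICC | Missing | T | R | SE ratio | SE ratio with small term |
|---|---|---|---|---|---|
| 0.03 | 15% | 0.0668 | 0.0596 | 0.945 | 0.938 |
| 0.03 | 25% | 0.0717 | 0.0599 | 0.914 | 0.908 |
| 0.04 | 15% | 0.0764 | 0.0669 | 0.935 | 0.928 |
| 0.04 | 25% | 0.0813 | 0.0655 | 0.898 | 0.891 |
| 0.05 | 15% | 0.0861 | 0.0741 | 0.928 | 0.919 |
| 0.05 | 25% | 0.0909 | 0.0711 | 0.885 | 0.877 |

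**Simulation**, no true effect, 17 providers of 31, SD 6.0 kg, 20 imputations by arm without provider, provider-level analysis:

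- Pooled SE over true SE: 0.94 and 0.92 at ICC 0.03 (15% and 25% missing); 0.92 and 0.87 at ICC 0.05. Error rates are 5.5 to 7.3%.
- A separate simulation (600 trials per setting, random-intercept analysis) compared the pooled SE with that of the mixed model on observed data. It was 5.7 to 6.6% smaller (15% missing) and 8.7 to 9.9% smaller (25%) at ICC 0.03 to 0.04, and 7.8% and 11.4% smaller at ICC 0.05. Coverage of the 95% interval at ICC 0.05 was 93.7% and 92.5%.
- With provider as a random effect in the imputation, the SE ratio was 1.00 to 1.02 and the error rate 4.3 to 4.9%.

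**Limits of the effect**, from simulation:

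- Inverse-probability weighting with a provider-clustered variance: SE within about 1 to 2% of the empirical SD at ICC 0.05.
- Least-favourable scenario, imputed without provider: pooled SE 1.05 to 1.18 times the true SE and error rates of 1.5 to 3.5%, so too wide. Filling PAL gaps from the control pattern shrinks the estimated difference by about (1 − f), so the estimate's own between-provider variance falls by the same (1 − f)² and no shortfall arises.

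**The case against.** The strongest reply is that the plan never excludes provider. It does not say that baseline characteristics are the sole input, and it does not limit them to Veterans' characteristics. The section on Statistical and Data Analysis checks whether "both providers' and Veterans' baseline characteristics are balanced between the intervention arms", so provider characteristics are in view. This stands as far as it goes: the gap is silence, and the shortfall is conditional on the imputation being run as described. But that sentence concerns balance checks, and measured provider characteristics would carry only the part of the provider effect that they explain.

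A reader might also infer three stronger things that the documents do not support:

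- *That the primary result is too precise.* It is not. The Aim 1 mixed model already allows for provider and needs no imputation under missing at random.
- *That weighting has the same fault*, because the quoted sentence covers both methods. Weighting creates no imputed values. It needs a provider-clustered variance, which the plan does not state, but that is a separate point.
- *That the plan's robustness check would falsely reassure.* For the one pattern-mixture scenario it names, the error runs the other way. The other scenarios are not named and cannot be assessed.

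Finally, at ICC 0.03 the cost is modest: an SE 6 to 8% too small in the simulation.

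**Conclusion.** The concern holds for the missing-at-random multiple imputation described in Data Analysis and in the Missing Data Analysis paragraph under Aim 3, and for nothing else. If provider is left out, those intervals are roughly 5 to 13% too narrow with 17 providers, ICC 0.03 to 0.05 and 15 to 25% missing. The error rate is then about 5.5 to 7.3% instead of 5%, whether or not the analysis model has a provider term. The top of the range needs ICC 0.05 and 25% missing. With 10 team clusters at ICC 0.05 the shortfall would be 10 to 15%; at ICC 0.01, about 3%.

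This assumes a two-sided 5% level, equal provider sizes, the same missing rate for every provider, and baseline variables that explain little of the weight change. The affected analyses are secondary, so the conclusion is a correction to the specification and not a challenge to the main comparison.

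**What to change.** In Data Analysis and in the Missing Data Analysis paragraph, state that the missing-at-random multiple imputation is multilevel, with provider as a random effect alongside arm and the baseline variables. A random effect is preferable to provider indicators: entered as fixed effects in the imputation, provider made the SE 5 to 10% too large at ICC 0.05.

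The cost is a sentence in the plan and a standard multilevel imputation routine, with no new data. The downside is that these secondary intervals become wider than the provider-free version would give, by about 1/0.94 = 1.06 to 1/0.87 = 1.15 times. That figure does not carry over to the least-favourable scenario, where the intervals are already too wide.
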